5.2. Patient-reported outcomes

The Knee Injury and Osteoarthritis Outcome Score (KOOS) and the Medical Outcomes Study Short Form-36 (SF-36) will be used to assess patient-oriented outcomes. The KOOS addresses knee performance and was designed and validated to monitor changes in outcome and the progression of OA following ligament and meniscal injuries⁵⁹. The KOOS is a self-administered questionnaire that evaluates treatment outcomes within 5-categories: 1) pain, 2) symptoms, 3) activities of daily living, 4) sports and recreation function, and 5) knee related quality of life. All questions within each category are scored on a 5-point scale. The scores within each category are added to produce a scoring profile (on a scale of 100 for each of the five categories) that can be followed over time. A 15-point decrease in the KOOS is equivalent to the difference between a “mild” and “moderate” deficit⁵⁹. Although all five scores are evaluated, those that are most sensitive to change after ACLR are the KOOS-quality of life and the KOOS-sports⁵⁹. These are expected to provide the greatest insight into the patient-oriented outcome of our patients. The SF-36 is a validated, self-administered instrument that is commonly used to monitor general health and to evaluate treatment effects in clinical studies⁷⁶. It assesses physical function, role limitations due to physical health issues, bodily pain, vitality, social functioning, mental health, and reported health transition.

5.3. Knee kinematics

A-P laxity: Passive laxity measurements^{24,27}, that are obtained with the leg muscles relaxed, are an important outcome since they assess ligamentous and capsular function, are predictive of the graft material properties^{6,44}, and correlate with radiographic change in ACL-deficient knees²⁶. The KT-1000 is the most reliable of the commercially available knee laxity measurement devices^{37,66}, and is used by the clinical coordinator to document A-P laxity. For this study, A-P laxity is defined as the amount of A-P directed translation of the tibia (relative to the femur) between the shear load limits of -90 N (posterior) and 133 N (anterior). A-P laxity (instead of anterior laxity) was selected since variability is reduced when sagittal plane laxity is referenced to a posterior shear load rather than zero load^{23,37}.

5.4. Dynamic joint function

Isokinetic strength testing is performed to assess the strength of the quadriceps muscles. Isokinetic strength of the quadriceps has been shown to be a predictor of the peak external flexion moments that is produced during jogging ($r^2 = 0.83$)^{16,55}. The clinical coordinator administers the tests using the Biodex System 3 (Biodex Medical Systems, Inc. Shirley NY) located in our research facility. The subjects are positioned on the

device with its axis of rotation aligned with the transepicondylar axis of the femoral condyles. The subjects perform the tests at 60°/sec¹⁶. Averaging the peak torques of five repetitions and normalizing these values with respect to bodyweight and height quantifies peak quadriceps strength. Both knees are tested. **Note: The isokinetic testing system failed after the 84-month follow-ups were completed. The system was not replaced and thus will not be used for the 12 and 15-year follow-up assessments.**

One-leg hop test is also performed to assess function^{61,78}. The subject performs the one-leg hop test for distance independently on each leg. Three trials for each are recorded and averaged. The difference in distance between the reconstructed and the normal knee is calculated.

5.5. Clinical outcome

Clinical outcome will be assessed using the International Knee Documentation Committee (IKDC) knee rating scale^{23,48}. The IKDC rating has been validated for ACLR⁴⁸. The IKDC scores evaluate four categories: 1) the patient's subjective assessment of function, 2) symptoms, 3) range of knee motion, and 4) clinical examination. The IKDC score rates knees as normal, nearly normal, abnormal, and severely abnormal, which can be transformed to an ordinal scale of 1 (normal) to 4 (severely abnormal). The final IKDC rating is then based on the score of the worst category⁴⁸. In addition, height, weight, body mass index, thigh circumference (6cm above joint line) and the number of recurrent injury episodes is recorded. A sports medicine physician and a physical therapist will continue to independently perform all of the pre- and post-operative clinical examinations.

6. Controlled Variables

Investigators have shown that the initial graft tension level required to restore normal knee laxity is specific to the graft material, cross-sectional area of the graft, and the free length of the graft between fixation sites¹⁵, and these were controlled in this study. Initially, subjects undergoing ACL reconstruction using a bone-patellar tendon-bone autograft were recruited to control the variability due to graft type. However, there has been a recent surge in the popularity of the 4-stranded hamstring tendon graft. Thus, we elected to recruit patients who were candidates for ACL reconstruction with 4-stranded hamstring autografts to increase our population base. This was justified because recent biomechanical studies have demonstrated that the structural properties of the patellar tendon autograft are equal to that of the 4-stranded hamstring tendon autograft⁷⁹. Likewise, the in-situ forces, the passive load-displacement response, and dynamic kinematics of reconstructed knees with patellar tendon and 4-stranded hamstring tendon grafts are similar^{68,82}. Finally, recent prospective randomized clinical trials have shown that functional outcome following ACL reconstruction with 4-stranded hamstring or patellar tendon autografts are equivalent^{2,3,19,33,34,41,42,49,57,62,64}.

The intra-articular position of the graft has been shown to affect the graft forces post-operatively, and was standardized in this study^{10,17,25,38,46}. A 2 mm deviation in femoral graft placement has been shown to have a pronounced effect on the graft elongation pattern⁴⁵. A graft that is placed to far anterior on the femur will cause it to get tight in flexion and slack in extension. Likewise, a graft that is placed in the "over-the-top" position will get tight in extension and slack in flexion. Thus, intra-articular graft position may influence the healing response^{9,70}. However, all the surgeons utilized the same drill guide system and anatomical landmarks to standardize graft position across subjects. Although variation may still exist, we have previously shown that they are equally distributed within each treatment group⁹.

Another standardized variable, which could possibly affect outcome, is the rehabilitation program prescribed following surgery⁸. Recent data comparing commonly used rehabilitation protocols suggest otherwise. We have shown that rehabilitation with either an "accelerated" or "non-accelerated" program produces the same outcome with respect to AP knee laxity, clinical assessment, patient satisfaction, functional performance, strength, and proprioception^{5,8}. In the current study, all subjects were required to follow the "accelerated" rehabilitation program. They received supervised post-operative physical therapy for a minimum of 16 weeks. Because the patients were randomly assigned to each treatment group, we feel that any deviation from the rehabilitation program (either produced by the patient's inability to keep up with the program, or the patient's unwillingness to follow the prescribed rehabilitation) was equally distributed between the two groups.

7. Protocol Summary

When a subject (either surgical or control) consents to continue their participation in the study, 144- and 180-month follow-up assessments will be performed. All patients have been previously enrolled into the study. However, the lay summary consent forms were based on an 84-month follow-up. Therefore, the subjects will need to be re-consented in order to participate in the extended study. The clinical coordinator will consent the patients after contacting them via mail with a phone call follow-up. Within the initial contact letter, a card will be provided so that the subject can let us know if they do not want us to contact them by phone.

The clinical examinations will occur at the sports medicine clinic of University Orthopaedics Inc. At the first visit (144 month), the subject will meet with the clinical coordinator to finalize the consent forms. Once the subject has granted informed consent, an X-ray technician will acquire the radiographs for the joint space width measurements. These will be obtained under the direction of the clinical coordinator who will make sure all the necessary steps required to reposition the patient relative to the x-ray system are taken. A research physical therapist will independently perform the clinical exam (IKDC). At this time, the clinical coordinator will administer the questionnaires (SF-36; KOOS; Tegner), the A-P laxity exam (KT-1000) and the functional assessment (One-leg hop). The clinical coordinator will also schedule the MRI examination, which will be performed at another site.

The MRIs will be performed at the MRI Research Facility at Brown University under the guidance of a certified MR technician. The scans (Table 4) will be performed using the TIMS Trio scanner. The scans will be WORM scored by a board-certified radiologist with expertise in musculoskeletal MR.

All subjects will be contacted by the clinical coordinator via phone each year that a visit is not scheduled. The primary reason for this will be to keep all of the subjects engaged in the study.

8. Statistical analyses

Treatment Comparisons - Primary Outcome Measure: Repeated measures analysis of variance will be used to evaluate differences among treatment groups with respect to temporal changes in joint space width (i.e. joint space narrowing). The statistical model will include fixed factors representing treatment group (“low-tension”, “high-tension” and “control”), limb (operative vs. contra-lateral or two controls), location (medial vs. lateral), time (baseline, 12-, 36-, 60-, and 84-month), and their interactions. If significant interactions are detected, simple effects will be compared using the Student-Newman-Keuls procedure based on the appropriate error terms⁸⁰. Because one of the repeated factors (i.e. time) is quantitative, orthogonal polynomial will be used to partition the time effect into its individual quantitative components (i.e. linear and quadratic). The significance of these orthogonal contrasts will be used to evaluate the linearity (or non-linearity) of the temporal trend associated with degeneration. Analyses will be performed using SAS, PROC MIXED⁵² that allows for covariance structures other than compound symmetry (e.g. unstructured, autoregressive, spatial power law). It is expected that the variability across subjects may increase across time due to only a subset of individuals exhibiting degeneration, which would violate the standard homogeneity of variance assumptions. The normality assumption will be examined based on residuals using normal probability plots and the Wilk-Shapiro test. If necessary, data will be transformed prior to analysis in order to satisfy the distributional assumptions.

Treatment Comparisons - Secondary Outcome Measures: Repeated measures analyses of variance will also be used to test for differences in secondary outcome measures corresponding to knee kinematics, dynamic function, patient reported outcomes, and clinical outcomes. For measures that are performed on each limb (e.g. A-P laxity), the statistical model will include fixed factors representing treatment group, limb, and time, along with their interactions. Repeated measures analyses on secondary outcome that are not limb-specific (e.g. KOOS and SF36) will include only treatment, time, and their interaction as factors. Post hoc analyses involving tests of simple effects and orthogonal polynomials will be similar to methodology previously described for joint space width. Because specific secondary outcome measures are assessed more frequently in the two experimental arms than in the control group (Tables 2&3), direct post hoc comparisons involving the two tension groups and examination of temporal trend in these group will utilize the additional assessments.

Relationship between A-P Laxity and Progression of OA: The longitudinal relationship between A-P laxity and progression of OA as measured by joint space narrowing (both radiographically and using MRI) will be examined in the context of hierarchical linear modeling¹³, also known as random coefficient modeling. Using data obtained from the experimental subjects, SAS PROC MIXED will be employed to examine the association between individual subjects' changes in A-P laxity with their changes in joint space width (radiography) or cartilage thickness (MRI). This will be accomplished by considering A-P laxity as a covariate (predictor) that would potentially change over time with joint space width and cartilage thickness being considered as the dependent measures. Individual subjects are modeled based on unique intercepts and slopes corresponding to time and the covariate. Across subject factors such as tension group, gender, graft type, and age will also be considered. A similar analysis will be performed to establish the relationship between isokinetic strength, KOOS, functional testing and OA progression.

Missing Visits and Subject Loss to Follow-up: Unlike traditional software used for repeated measures analyses (e.g. SAS PROC GLM and BMDP -2V), PROC MIXED appropriately handles incomplete data due to missed visits without completely excluding subjects from the analysis. The pattern of missing data is assumed to be random, which in-practice, is likely to be violated to some degree. We will test for differences in the rate of missed visits across treatment groups and across time using categorical repeated measures (SAS, PROC CATMOD). The proportion of subjects that are loss to follow-up will be compared across treatment and control arms using a chi square test. Though we are finding that missed visits are infrequent and most likely equally distributed across treatment groups, we will examine whether specific baseline characteristics that may be predictive of outcome are also associated with missed visits using logistic regression. We recruited 54 subjects per group in an effort to have 46 assessable subjects per group at the three-year follow-up visit based on the estimated 15% dropout rate. We have more than met this goal (3% drop out in our treatment groups and 15% drop out in our control group at 3 years. For the proposed 180-month follow-up, we expect that we will have at least 35 patients/subjects in each group (20% drop out rate of subjects currently enrolled).

Justification of Sample Size based on Primary Outcome Measure: The estimated sample size of 35 assessable subjects per group through the 84-month study period will result in having sufficient power ($1-\beta=0.80$ using $\alpha=.05$) to detect a mean difference between groups of 0.25 mm in joint space narrowing over the 84-month study period. This estimated difference is based on the following rationale. Previous studies have shown that patients with primary OA exhibit an estimated 0.3-mm change in joint space width per year^{51,63}. Since we will be studying patients at the time of OA onset, we will assume that patients who undergo initial changes will exhibit an average joint space narrowing of 0.1 mm per year, or a total of approximately 0.6 mm over the 84 months. This estimate was conservatively adjusted based on the study by Johma et al, who found that only 50% of the subjects that undergo ACL reconstruction after injury exhibit early degenerative changes following surgery⁵⁰. After taking into account that only a subset of subjects randomized may exhibit OA, the resulting mean difference is decreased to be 0.25-0.30 mm over the 84-month study period. An additional consequence of only a subset of the patients that are randomized exhibiting degeneration is an increase in the variability encountered across subjects with respect to joint space narrowing. The variability estimate used in our computations ($\sigma_{\Delta}=0.35$ mm) resulted from increasing the estimate derived from the literature for a group of subjects with OA in order to reflect our expected mixture of two subsets of subjects. Based on each subset having $\sigma_{\Delta}=0.20$, with 50% of the patients exhibiting narrowing a total of 0.6 mm and 50% showing no degeneration, the resulting overall estimated $\sigma_{\Delta}=0.35$. Assuming joint space width at baseline is approximately 4.5 mm³⁰, this detectable mean difference (0.25 mm) represents an approximate 5% change between the treatment groups in the mean rate of degeneration. We recruited 54 subjects per group in an effort to have 46 assessable subjects per group at the three-year follow-up visit based on the estimated 15% dropout rate^{4,7}. We have more than met this goal (3% drop out in our treatment groups and 15% drop out in our control group at 3 years). For the proposed 180-month follow-up we expect that we will have at least 35 patients/subjects in each group (20% drop out rate of subjects currently enrolled).

Power for Secondary Outcome Measures: Having determined the number of subjects needed to have sufficient power to detect expected differences in joint space narrowing, we computed the magnitude of the detectable difference for the main secondary outcome measures. These estimates are based on our previous data and values found in the literature. When the estimates were based on cross-sectional data from the literature (i.e. isokinetic strength), moderate correlation across time was assumed ($r=0.50$). The following mean differences correspond to the estimated power=0.80 and $\alpha=.05$ with the proposed sample sizes: A-P laxity =

1.25 mm (a 16% change relative to the normal A-P laxity value ⁷²); isokinetic knee strength = 18.5 Nm (a 12% change relative to normal, a “mild” deficit ¹⁶); KOOS- QOL score = 10.5 (a 10% change relative to full scale, considered less than a mild deficit ⁵⁹); KOOS-sports score = 10.1 (a 10% change relative to full scale, considered less than a mild deficit ⁵⁹), and IKDC score = .50 (a 12% change relative to normal ⁴⁸).

Note (9/29/2017): The 7 year data were completed and published in the American Journal of Sports Medicine in January 2016 (<http://www.ncbi.nlm.nih.gov/pubmed/27159308>). The study was extended to 12 and 15 years and the data collection for these time points is currently underway.

REFERENCES

1. Aickin M. A program for balancing the allocation of subjects in a clinical trial. *Computational Biomed Res.* 1982;15:519-524.

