Initial Graft Tension and ACL Surgery

PI: [name]

**Rhode Island Hospital
Providence RI 02903**

ClinicalTrials.gov identifier: NCT00434837

Updated: 09/10/2019 (after NIH funding received for 15-year follow-up; R01-AR074973)

SPECIFIC AIMS

The primary objective of this prospective, randomized, double-blinded, controlled study is to assess OA progression following ACL reconstruction (ACLR), and to determine how the initial tension applied to the graft at the time of surgery may influence disease progression. ACLR is commonly performed to restore joint function and to decrease the risk of post-traumatic osteoarthritis (OA) in the ACL-deficient knee. However, clinical studies suggest that the outcome is highly variable, and that OA often progresses despite ACLR. The tension applied to the graft at the time of ACLR fixation (“initial graft tension”) affects knee kinematics and the distribution and magnitude of contact stress, which in turn, is thought to influence articular cartilage damage. The effects of low- and high-initial graft tensions on graft healing and articular cartilage degeneration following ACLR are unknown and are currently under investigation in this study. Over the past funding cycle, ACL-injured subjects (108 patients) and matched controls (60 subjects) were recruited and enrolled. Short-term (≤ 84 months) post-surgical evaluations have been performed. The objective of this update is to prospectively obtain valuable long-term (15 year) follow-ups on this captured patient/control population. We intend to follow these patients a minimum of 15 years. These long-term data will allow us to establish not only the incidence of OA after ACLR following an isolated ACL tear, but whether changing the initial graft tension can decrease this risk.

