This study is designed to compare two common initial graft tension protocols for ACLR that influence joint contact mechanics. The first treatment group consists of patients whose grafts were tensioned to restore the normal anterior-posterior displacement of the tibia relative to the femur (“AP laxity”) at the time of surgery (i.e. AP laxity equal to that of the contralateral normal knee; the “low-tension” treatment). The second treatment group consists of patients whose grafts were tensioned to over-constrain the joint (i.e. AP laxity 2mm less than that of the contralateral knee; the “high-tension” treatment). In the last funding cycle, we have shown that the initial joint contact conditions between these two groups are significantly different in cadavers³⁹, and that the associated laxity differences in patients are different *in vivo*. The two treatment groups are being compared to a third matched control group. Fifty-four subjects were enrolled into each group. With this update, they will be followed 180 months after surgery. We are planning to follow these patients for a minimum of 15 years. Significant changes in cartilage integrity are expected within this long-term time frame in this patient population^{26,35,50}.

Radiographic assessment of joint space narrowing is the only validated indicator of structural change used to evaluate OA progression in clinical studies, and it will continue to be the primary outcome measure of cartilage damage⁶⁷. MR images of the articular cartilage and associated knee joint structures will provide secondary structural biomarkers for the early detection of OA³¹. MRI is being used to directly measure changes in cartilage thickness in the load bearing regions^{11,12}, while joint integrity will be assessed using the Whole Organ Magnetic Imaging Score (WORM score)⁵⁶. Using these imaging-based outcome measures, we will test the primary hypothesis:

- *Tibiofemoral joint space width (via radiography) and cartilage thickness (via MRI) in the reconstructed knees of the “high-tension” treatment group will be equal to that of the control group, while the joint space width and cartilage thickness in the “low-tension” treatment group will be significantly less than that of the control group 15 years after surgical reconstruction of the anterior cruciate ligament.*

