Surgical outcome will also be assessed via: 1) patient-oriented outcome scores^{59,76}, 2) AP laxity (an indicator of graft integrity^{6,44} and knee kinematics²³), 3) isokinetic strength (an indicator of dynamic knee function¹⁶), and 4) clinical outcome scores^{48,78}. Analysis of primary and secondary outcomes will enable us to determine the long-term effects of initial graft tension on cartilage status and knee joint function, and to evaluate the relationships between longitudinal changes that occur in tibiofemoral (TF) joint space (x-ray), cartilage thickness (MRI), general MRI scores (WORM score), knee laxity (KT-1000), strength (Biodex strength test, 1 legged hop test) and patient-oriented outcome scores (SF-36, Knee Osteoarthritis Outcome Score). In the past funding cycle, data were obtained from ACL-reconstructed patients pre-operatively, immediately post-operatively, and after 6, 12, 36, and 84 months of healing. From the control group data were obtained at the time of recruitment and at 12, 36, and 84 months. In this update, additional evaluations will be performed 144 and 180 months in the ACLR and control subjects, a time frame in which cartilage damage should become prevalent in the ACLR patient population. We intend to follow these patients for a minimum of 15 years.

RESEARCH DESIGN AND METHODS

1. Overview of Research Design

This investigation is designed as a prospective, randomized, double-blinded clinical study evaluating the effects of two different initial tension conditions applied to an ACL graft at the time of fixation on healing using biomechanical, clinical, and patient-oriented outcome measures. The primary outcome is evaluating the progression of OA via objective radiographic measurements of joint space narrowing. We are also assessing temporal changes in cartilage thickness, and the integrity of various knee joint structures using MRI. We will test the hypothesis that tibiofemoral (TF) joint space width (via radiography) and cartilage thickness (via MRI) in the reconstructed knees of the “high-tension” treatment group will be equal to that of the control group, while the joint space width and cartilage thickness in the “low-tension” treatment group will be significantly less than that of the control group 15 years after surgical reconstruction of the ACL. We intend to follow these patients for a minimum of 15 years.

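### The primary hypothesis is set at 15 years, but the primary model's time factor and the sample-size justification both stop at 84 months

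*Combined protocol and SAP*

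**What the plan says.** The title block dates the document to the extension: "Updated: 09/10/2019 (after NIH funding received for 15-year follow-up". The Specific Aims set the primary hypothesis against the "control group 15 years after surgical reconstruction of the anterior cruciate ligament", and section 1 repeats that time point. The Specific Aims also say that "additional evaluations will be performed 144 and 180 months in the ACLR and control subjects". In section 7, at the 144-month visit, "an X-ray technician will acquire the radiographs for the joint space width measurements".

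Section 8, under the primary outcome measure, specifies a mixed-model repeated-measures analysis with group, limb, location and "time (baseline, 12-, 36-, 60-, and 84-month), and their interactions". Linear and quadratic contrasts are taken over that time factor. On follow-up comparisons it says: "If significant interactions are detected, simple effects will be compared using the Student-Newman-Keuls procedure".

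The sample-size justification claims 80% power at alpha 0.05 with 35 assessable subjects per group "to detect a mean difference between groups of 0.25 mm in joint space narrowing over the 84-month study period". For 180 months, section 8 gives only expected retention of at least 35 per group.

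**The concern.** The hypothesis names the outcome, the groups and the time. The primary analysis omits that time. With the listed levels, the group-by-time test and the polynomial time contrasts describe change up to 7 years, and neither extension visit enters the model.

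Adding the two levels is simple, but it does not settle everything. A comparison of groups at one visit is a simple effect, and the plan makes simple effects only after a significant interaction. So a 180-month comparison would still not be guaranteed, and the difference it is meant to detect would still be unspecified. The note dated 9/29/2017 in section 8 says that the 7-year results are published and that 12- and 15-year data are being collected. Choices left open now would be made while the deciding data accrue.

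**Working it through.** **Time points side by side**

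- Hypothesis (Specific Aims; section 1): 180 months.
- Planned extension visits (Specific Aims; sections 1 and 7): 144 and 180 months.
- Primary model (section 8): 0, 12, 36, 60 and 84 months.
- Sample-size justification (section 8): 84 months.
- Share of follow-up after the model's last level: (180 − 84)/180 = 53%.

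The model also has a 60-month level, whereas the visits listed in the Specific Aims are at 6, 12, 36 and 84 months for patients and 12, 36 and 84 months for controls. Tables 2 and 3 are not in the text available to us and may explain this.

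**Reproducing the 84-month figure**

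Inputs from the sample-size justification: 35 per group, alpha 0.05 (two-sided assumed, since sidedness is not stated), power 0.80. Half the patients narrow by 0.6 mm and half by nothing, with SD 0.20 mm within each subset.

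- Mixture SD = √(0.20² + 0.5 × 0.5 × 0.6²) = √0.13 = 0.361 mm. The plan uses 0.35 mm.
- For a two-sample t-test with 35 per group, the difference detectable with 80% power is 0.679 × SD. This is 0.238 mm (SD 0.35) or 0.245 mm (SD 0.361), against 0.25 mm stated.
- Power for 0.25 mm is 84% (SD 0.35) or 82% (SD 0.361), against 80% stated.

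The 84-month figure is therefore sound and slightly conservative.

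**Illustration at 180 months**

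The plan gives no effect size or SD for 180 months. What follows assumes linear narrowing, the same 50% mixture, 35 per group and equal SDs in both groups.

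The plan describes its rate in affected patients as "average joint space narrowing of 0.1 mm per year, or a total of approximately 0.6 mm over the 84 months". Since 0.1 × 7 = 0.7, these two figures do not quite agree, so both are carried forward:

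- 0.6 × 180/84 = 1.29 mm in progressors;
- 0.1 × 15 = 1.5 mm in progressors.

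The subset SD is either held at 0.20 mm or scaled to 0.20 × 180/84 = 0.429 mm. The target keeps the plan's ratio of 0.25 mm to 0.6 mm, giving 0.25/0.6 × 1.29 = 0.536 mm and 0.25/0.6 × 1.5 = 0.625 mm. The mixture SD is √(subset SD² + (progressor loss/2)²).

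| Loss in progressors | Subset SD | Mixture SD | Detectable difference (80% power) | Target | Power |
|---|---|---|---|---|---|
| 1.29 mm | 0.20 | 0.673 | 0.457 mm | 0.536 mm | 91% |
| 1.29 mm | 0.429 | 0.773 | 0.525 mm | 0.536 mm | 82% |
| 1.5 mm | 0.20 | 0.776 | 0.527 mm | 0.625 mm | 91% |
| 1.5 mm | 0.429 | 0.864 | 0.587 mm | 0.625 mm | 85% |

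The SD roughly doubles and the detectable difference with it. Power depends on the target, which the plan does not give.

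**The case against.** The strongest reply is that this is carried-over text. The 15-year intent is plain throughout. The cartilage-thickness text in section 5.1 shows the same slip, planning scans at 144 and 180 months and then registering images at 0, 36, 60 and 84 months. The outcome, groups, factors, software and expected 180-month numbers are all stated, and adding two levels to the model would yield 180-month means. Section 3 also commits to analysing all available data. Much of this stands, and it is why the repair is cheap. But the all-available-data sentence deals with graft failure, missing tests and dropout; it neither changes an explicit list of levels nor names a contrast.

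It is also fair to say that testing interactions first and simple effects second is a recognised strategy. A reader might infer that every group comparison depends on an interaction. The text does not say so: the model tests group and group-by-time effects in any case, and only simple effects are conditional. Nor is a multiple-comparison procedure absent, since Student-Newman-Keuls is named for simple effects. What is open is whether it covers 180-month contrasts once they are specified.

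A reader might further infer that the trial is underpowered at 15 years. The documents do not support that. Low power appears if the 0.25 mm target is kept while the SD grows (22% to 33% for the four SDs above), but the plan sets that target for 84 months only.

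**Conclusion.** The plan is wrong as written on this point. Its primary hypothesis is at 180 months, and its primary model and sample-size justification end at 84 months, so the primary analysis followed literally does not test the hypothesis at its own time point. Nothing elsewhere in the document repairs this. The conclusion rests on the text alone and needs no power argument.

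The power figures only show that the 84-month statement cannot simply be reused. They depend on linear narrowing, an unchanged 50% mixture, equal SDs, a two-sided test and no multiplicity adjustment. On those assumptions power is about 82% to 91%. The proper statement is that 180-month power is unspecified.

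**What to change.** 1. In the primary-outcome paragraph of section 8, add 144 and 180 months to the time levels, and reconcile the 60-month level with the visit list in the Specific Aims.
2. Name the 180-month contrasts that address the hypothesis: change in joint space width from baseline, each tension group against control. Report them with 95% confidence intervals whether or not an interaction is significant, and state whether Student-Newman-Keuls or another procedure covers them. Also report the randomised low- versus high-tension contrast at 180 months; its rank is for the sponsor to decide. State that a non-significant difference between high tension and control will not be read as showing that the two are equal.
3. In the sample-size justification, restate the detectable difference or power at 180 months with 35 per group and an SD suited to 15 years.

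These choices should be fixed before the 144- and 180-month data are compared by group. The cost is wording and one power calculation; no new visits or data are needed.
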